11.3 Clinical Site Monitoring and Record Availability

11.3.1 Site monitors under contract to the NIAID will visit participating clinical research sites to review the individual participant records, including consent forms, CRFs, supporting data, laboratory specimen records, and medical records (physicians' progress notes, nurses' notes, individuals' hospital charts), to ensure protection of study participants, compliance with the protocol, and accuracy and completeness of records. The monitors also will inspect sites' regulatory files to ensure that regulatory requirements are being followed and sites' pharmacies to review product storage and management.

11.3.2 The site investigator will make study documents (eg, consent forms, drug distribution forms, CRFs) and pertinent hospital or clinic records readily available for inspection by the local IRB, the site monitors, the NIAID, and the OHRP for confirmation of the study data.

11.4 Expedited Adverse Event Reporting to DAIDS

11.4.1 Adverse Event Reporting to DAIDS

Requirements, definitions and methods for expedited reporting of Adverse Events (AEs) are outlined in Version 2.0 of the DAIDS EAE Manual, which is available on the RSC website at <http://rsc.tech-res.com/safetyandpharmacovigilance/>.

The DAIDS Adverse Events Reporting System (DAERS), an internet-based reporting system, must be used for expedited AE reporting to DAIDS. In the event of system outages or technical difficulties, expedited AEs may be submitted via the DAIDS EAE Form. For questions about DAERS, please contact DAIDS-ES at [contact]. Site queries may also be sent from within the DAERS application itself.

Sites where DAERS has not been implemented will submit expedited AEs by documenting the information on the current DAIDS EAE Form. This form is available on the RSC website: <http://rsc.tech-res.com/safetyandpharmacovigilance/>. For questions about EAE reporting, please contact the RSC ([contact]).

11.4.2 Reporting Requirements for this Study

- The SUSAR Reporting Category, as defined in Version 2.0 of the DAIDS EAE Manual, will be used for this study.
- The study agent for which expedited reporting is required is depot medroxyprogesterone acetate (DMPA).
- In addition to the EAE Reporting Category identified above, other AEs that must be reported in an expedited manner are: Injection related AEs.

11.4.3 Grading Severity of Events

The Division of AIDS Table for Grading the Severity of Adult and Pediatric Adverse Events (DAIDS AE Grading Table), Version 1.0, December 2004 (Clarification, August 2009), must be used and is available on the DAIDS RSC Web site at <http://rsc.tech-res.com/safetyandpharmacovigilance/>. This table will be used for all genital and menstrual symptoms.

11.4.4 Expedited AE Reporting Period

- The EAE reporting period for this study is as per the EAE manual.
- After the protocol-defined AE reporting period, unless otherwise noted, only suspected, *unexpected* serious adverse reactions (SUSARs), as defined in Version 2.0 of the EAE Manual, will be reported to DAIDS if the study staff become aware of the events on a passive basis (from publicly available information).

12.0 HUMAN PARTICIPANTS

12.1 Institutional Review Board (IRB) Review and Informed Consent

This protocol and the informed consent document (Appendix I) and any subsequent modifications will be reviewed and approved by the IRB or ethics committee responsible for oversight of the study. A signed consent form will be obtained from the participant. The consent form will describe the purpose of the study, the procedures to be followed, and the risks and benefits of participation. A copy of the consent form will be given to the participant, and this fact will be documented in the participant's record.

12.2 Participant Confidentiality

All laboratory specimens, evaluation forms, reports, and other records that leave the site will be identified by coded number only to maintain participant confidentiality. All records will be kept locked. All computer entry and networking programs will be done with coded numbers only. Clinical information will not be released without written permission of the participant, except as necessary for monitoring by the ACTG, IRB/EC, NIAID, and OHRP, or other government agencies as part of their duties.

12.3 Study Discontinuation

The study may be discontinued at any time by the ACTG, IRB/EC, NIAID, or the OHRP, or other country-specific government agencies as part of their duties to ensure that research participants are protected.

13.0 PUBLICATION OF RESEARCH FINDINGS

Publication of the results of this trial will be governed by ACTG policies.

14.0 BIOHAZARD CONTAINMENT

As the transmission of HIV and other blood-borne pathogens can occur through contact with contaminated needles, blood, and blood products, appropriate blood and secretion precautions will be employed by all personnel in the drawing of blood and shipping and handling of all specimens for this study, as currently recommended by the Centers for Disease Control and Prevention and the National Institutes of Health.

All dangerous goods and materials, including diagnostic specimens and infectious substances, must be transported using packaging mandated by CFR 42 Part 72. Please refer to instructions detailed in the International Air Transport Association (IATA) Dangerous Goods Regulations.

Statistical Analysis Plan

**ACTG A5338: An Open-Label, Non-Randomized Study of
Pharmacokinetic Interactions Among Depot Medroxyprogesterone Acetate
(DMPA), Rifampicin (RIF), and Efavirenz (EFV) in Women Co-Infected
with Human Immunodeficiency Virus (HIV) and Tuberculosis (TB)**

ClinicalTrials.gov Identifier: NCT02412436

**Version 1.0
November 28, 2018**

Introduction

This Statistical Analysis Plan addresses the following secondary objectives listed in the study protocol.

1.3.1. To estimate the area under the concentration-time curve (AUC), trough concentration (C_{\min}), maximum concentration (C_{\max}), apparent clearance (CL/F), and half-life ($t_{1/2}$) of MPA in HIV and TB coinfecting women taking EFV-based cART and RIF-containing TB treatment.

1.3.2. To estimate time and variability in time to MPA C_{\min} reaching 0.1 ng/mL or less in HIV and TB coinfecting women taking EFV-based cART and RIF-containing TB treatment.

Statistical Analysis Plan

- The concentration vs. time data for DMPA will be analyzed using nonlinear mixed-effects (NLME) modelling using the software NONMEM (version 7.4.2) (S. Beal, Sheiner, Boeckmann, & Bauer, 2009) pooling the data from the available studies A5338, A5238 and A5093.
- The modelling approach followed a stepwise procedure to first identify the structural model best describing the data, and then incorporate the effect of the study covariates such as weight, age, and effect of concomitant anti-retroviral and anti-tuberculosis treatment.
- Various structural pharmacokinetic models were evaluated, focusing on correctly characterizing the absorption after intra-muscular injection. The tested models included one and two compartments disposition, with first-order elimination and zero-, first-order, two parallel first order absorption.
- Model selection was based on changes in the NONMEM objective function value (Δ OFV), and visual inspection of conditional weighted residuals (CWRES) versus time, visual predictive checks, and basic goodness of fit plots (GOF).
- Statistically significant variability and correlation estimates for the PK parameters were included and the covariates of interest were retained in the final model with respect to their impact on the PK parameters and their variability. Covariate selection was based on the drop in objective function value (assumed to be χ -square distributed and thus using 3.84 points drop as significant at $p < 0.05$ for the inclusion of a single parameter), while scrutinizing the physiological plausibility of the effect.
- Allometric scaling (Anderson & Holford, 2008) was USED to account for the effect of body size on the pharmacokinetic parameters, using total body weight.

References

2. Anderson, B. J. & Holford, N. H. G. Mechanism-Based Concepts of Size and Maturity in Pharmacokinetics. *Annu. Rev. Pharmacol. Toxicol.* **48**, 303–332 (2008).

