10.1 Pharmacology Objectives

Using nonlinear mixed-effects (NLME) modeling, the population PK of MPA will be described in the population in order:

10.1.1 To describe the structural PK model for MPA given in the DMPA formulation.

10.1.2 To identify and quantify the effects of covariates influences on PK (eg, weight [including total, fat and lean components], age, time on TB treatment, time on ART, adherence to ART and TB treatments, CYP2B6 genotype, etc.).

10.1.3 To characterize between subject and random unexplained components of the PK variability.

10.1.4 To predict the time at which the proportion of women with MPA <0.1 ng/L matches that at 12 weeks from historical data.

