10.3 Primary and Secondary Data, Modeling, and Data Analysis

The concentration vs. time data for DMPA will be analyzed using NLME modelling using the software NONMEM (Version 7.2) [57].

The modelling approach will follow a stepwise procedure to first identify the structural model best describing the data, and then incorporate the effect of the study covariates such as weight, age, and effect of concomitant anti-retroviral and anti-tuberculosis treatment.

Various structural pharmacokinetic models will be evaluated, focusing on correctly characterizing the absorption after intra-muscular injection. The tested models will include one, two, and three compartments disposition with first-order elimination and zero-, first-order, or saturable absorption.

Statistically significant variability and correlation estimates for the PK parameters will be included and the covariates of interest will be evaluated with respect to their impact on the PK parameters and their variability.

Allometric scaling [59] will be used to account for the effect of body size on the PK parameters, using total body weight or fat-free mass. Other covariate effects will be evaluated and included if they significantly improve the ability of the model to describe the data. The effect of adherence to and time on ART and TB regimens, and CYP2B6 genotype (if available), will be investigated on clearance.

Concentrations below the limit of quantification will be included in the analysis and handled with established methods [60].

The tools used for model development and graphical and statistical diagnostics will include Xpose, and Perl Speaks NONMEM, and Pirana [61].

The PK profiles will be analyzed using post-hoc Bayesian methods to extract information such as peak concentration, overall exposure (AUC), and time above target concentration. Simulations will be employed to explore the pharmacokinetic profiles, their variability in a population, and how they are affected by weight, concomitant anti-retroviral or anti-tuberculosis treatment, other covariates found significant, and possibly under different dosing scenarios, and to predict the time at which the proportion of women with MPA <0.1 ng/L matches that at 12 weeks from historical data.

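### The pooled population model puts the EFV/RIF treatment effect, which is the trial's own hypothesis, through the same 3.84-point in-or-out rule as age; it should be kept in and reported with a CI

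*SAP*

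**What the plan says.** The SAP's Introduction limits it to secondary objectives 1.3.1 (MPA exposure, clearance and half-life) and 1.3.2 (time to 0.1 ng/mL). Its method is a nonlinear mixed-effects model pooling A5338, A5238 and A5093.

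- **Order of work.** "The modelling approach followed a stepwise procedure to first identify the structural model best describing the data, and then incorporate the effect" of covariates. These are described as "study covariates such as weight, age, and effect of concomitant anti-retroviral and anti-tuberculosis treatment".
- **Inclusion.** The rule rests on the objective function, "thus using 3.84 points drop as significant at" p < 0.05 "for the inclusion of a single parameter", applied "while scrutinizing the physiological plausibility of the effect".
- **Retention.** "the covariates of interest were retained in the final model with respect to their impact on the PK parameters and their variability". No number is attached.
- **Body size.** Total body weight enters by allometric scaling.

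Protocol 10.1.2 sets the aim "To identify and quantify the effects of covariates influences on PK" and names age, time on TB treatment, time on ART, adherence to each, and CYP2B6 genotype, besides weight. Section 10.3 looks at time on regimen, adherence and genotype on clearance. It then plans simulations by weight, concomitant treatment, "other covariates found significant, and possibly under different dosing scenarios". Section 10.4 uses simulation to predict dosing frequency.

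Neither document states a backward step, a multiplicity allowance, or the number of covariate-parameter pairs tested.

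**The concern.** Protocol 1.1 hypothesises that EFV with RIF raises MPA clearance. That effect is the quantity to be estimated, whereas age or time on ART are adjustments. The SAP gives them equal standing: each is in or out according to a 3.84-point fall, and nothing commits the analysts to reporting the treatment effect if it falls short.

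In a model of A5338 alone, dropping the term would do little harm, because every participant takes both drugs. In a pooled model it matters. Without the term, A5338 women and historical women share one typical clearance. The estimates for objectives 1.3.1 and 1.3.2 then move toward women not on this combination, and any simulation from the model moves with them. If instead the term is shown only when it passes, the reported value is biased away from zero.

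A lesser matter is that an unadjusted 5% test per parameter, repeated over several candidates, can admit a covariate with no real effect, which the protocol would then carry into its simulations.

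**Working it through.** **1. The SAP's threshold.** The 0.95 quantile of chi-square on 1 df is 3.8415, and the p-value at 3.84 is 0.0500. The stated figure is correct.

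**2. Effect of the filter on the treatment estimate.** Let z = estimate/SE, roughly normal with mean d (true effect in SE units) and variance 1. The rule keeps the term when |z| > 1.96. Ignoring the negligible opposite tail:

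- P(kept) = Φ(d − 1.96)
- mean of z when kept = d + φ(d − 1.96)/Φ(d − 1.96)

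The documents give no SE for this term, so d is assumed.

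- d = 2: P(kept) = Φ(0.04) = 0.516. Mean when kept = 2 + 0.3986/0.516 = 2.77, and 2.77/2 = 1.39. The term is dropped about 48% of the time and overstated on average by 39% when kept.
- d = 3: P(kept) = Φ(1.04) = 0.851. Mean when kept = 3 + 0.2323/0.851 = 3.27, and 3.27/3 = 1.09. The term is dropped about 15% of the time and overstated by 9% when kept.

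**3. Size of the pull if the term is dropped.** The documents do not allow an exact figure. As an illustration, take 42 evaluable A5338 women and the 79 PK-evaluable women that protocol 9.4 counts in A5093 and A5283. Assume these 79 are the ones pooled (the SAP writes A5238) and that each woman carries equal weight. A5338 then supplies 42/(42 + 79) = 0.35 of the data. A single typical log-clearance would lie about 35% of the way from the historical value to the A5338 value.

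**4. Spurious inclusion.** With m independent tests of null covariates at 5%, P(at least one) = 1 − 0.95^m. The number of tests is not given, so the named lists are counted, one test per candidate:

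| Candidates counted | m | At 3.84 points | At 6.63 points (p < 0.01) |
|---|---|---|---|
| SAP list without weight | 3 | 14.3% | 3.0% |
| SAP list with weight | 4 | 18.5% | 3.9% |
| Protocol 10.1.2 without weight | 6 | 26.5% | 5.9% |
| Both lists without weight | 8 | 33.7% | 7.7% |
| Both lists with weight | 9 | 37.0% | 8.6% |

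The rows for 3, 4, 8 and 9 count the ART and TB treatment effects as if they were null, which they are not expected to be. The cleanest count leaves out both weight and treatment: the six protocol candidates, 26.5%. If only the candidates named in the SAP were tested, age alone would remain, at 5%.

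Positive correlation between tests lowers the figures. For 7 tests, 30% under independence becomes 27% at correlation 0.3 and 23% at 0.5. The chance passes one half only at 14 independent tests (51.2%; 13 give 48.7%).

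**The case against.** The strongest reply is that the trial's question does not rest on this model. The primary test in protocol 9.6.1 is a binomial proportion against 6%. The same section estimates the time to 0.1 ng/mL with a 90% CI from individual and mixed-effects fits without covariate selection. Section 9.6.2.1 gives geometric mean ratios with 90% CIs against the A5093 control arm, also unfiltered. Section 10.0 calls the population model secondary, and the SAP withdraws none of this. All of that stands and limits the harm. It does not correct the pooled model through which the SAP addresses objectives 1.3.1 and 1.3.2, or the simulations in 10.3 and 10.4.

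A second reply is that a large RIF effect would pass 3.84 points easily and be little inflated. That is true, but it is a reason to expect little change from keeping the term, not a reason to filter it. A separate ART effect may be smaller.

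Some stronger readings are tempting and should not be drawn:

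- **That every covariate reaching 3.84 points is kept.** The same SAP sentence adds a plausibility check, and another speaks of retention by impact. Neither has a stated criterion or known error rate, but both exist. Model selection also uses residual plots and visual predictive checks.
- **That backward elimination was ruled out.** The SAP is silent; it does not say so.
- **That a spurious covariate is likely.** On the named lists the chance is below one half. A count such as 21 pairs would give 66%, but no such count appears in either document, and protocol 10.3 ties most of its candidates to clearance alone.
- **That the simulated times are shown to be biased by spurious covariates.** The SAP does not mention simulations, and the size of any shift cannot be worked out from the documents.

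**Conclusion.** The concern holds for the treatment effect. The SAP lets a significance rule decide whether the effect under study appears in a model that pools the trial with historical women. The consequence is attenuation if the term is dropped and overstatement if it is reported only when significant: about 39% at a true effect of 2 SE and 9% at 3 SE. Those sizes rest on a normal approximation and assumed SE multiples.

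For the other covariates the concern is modest: roughly 14% to 37% across the ways of counting the lists, 26.5% on the cleanest count, assuming independent null tests, one per candidate, and no credit for the plausibility check. It would be higher if candidates were tried on several parameters, a number the documents do not give.

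The issue affects a secondary analysis and its simulations. It does not affect the primary test.

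**What to change.** Keep the EFV/RIF treatment effect on MPA clearance in the pooled model whatever its p-value, report the estimate with a CI, and carry it into the simulations. Because every A5338 participant takes both drugs, the contrast is largely between studies and should be described as such.

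Optionally, as a sensitivity analysis, list the covariate-parameter pairs tested and say whether the other covariates survive backward elimination at 6.63 points (p < 0.01). This second part is a common choice, not a requirement.

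The cost is a few more NONMEM runs and a short addition to the report; the stricter retention step may lose a weak true covariate. Much of the SAP is in the past tense, so the modelling may already be done. In that case the change is a rerun with the term retained and fuller reporting.
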